5.4.2 Permitted Therapy

Subjects are permitted to use topical, ocular, intra-articular, intranasal, and inhalational corticosteroids (with minimal systemic absorption). Adrenal replacement steroid doses > 10 mg daily prednisone are permitted. A brief (less than 3 weeks) course of corticosteroids for prophylaxis (eg, contrast dye allergy) or for treatment of non-autoimmune conditions (eg, delayed-type hypersensitivity reaction caused by a contact allergen) is permitted.

Steroid use should be minimized prior to inclusion. Systemic corticosteroid use or physiologic replacement doses of steroids are permitted, even if > 20 mg/day prednisone equivalents, for: a) treatment-related AEs or b) treatment of non-autoimmune conditions (eg, prophylaxis for contrast dye allergy, contact hypersensitivity). Details regarding corticosteroid use prior to and during the study will be collected (name of medication, doses utilized, start and stop dates, frequency of use, route of administration). Information regarding concomitant corticosteroid use may be analyzed with regard to study outcome measures. Subjects requiring chronic treatment with corticosteroids should be treated with histamine-2-receptor antagonists or proton pump inhibitors as prophylaxis for potential gastrointestinal adverse reactions (ulceration, perforation, hemorrhage) unless otherwise contraindicated.

Concomitant medications are recorded at baseline and throughout the treatment phase of the study in the appropriate section of the CRF. All medications (prescriptions or over the counter medications) continued at the start of the study or started during the study and different from the study drug must be documented in the concomitant therapy section of the CRF.

All treatments that the Investigator considers necessary for a subject's welfare may be administered at the discretion of the Investigator in keeping with the community standards of medical care. All concomitant medication will be recorded on the case report form (CRF) including all prescription, over-the-counter (OTC), herbal supplements, and IV medications and fluids. If changes occur during the trial period, documentation of drug dosage, frequency, route, and date may also be included on the CRF.

All concomitant medications received within 28 days before the first dose of trial treatment and 30 days after the last dose of trial treatment should be recorded. Concomitant medications administered after 30 days after the last dose of trial treatment should be recorded for SAEs.

5.5 Subject Withdrawal/Discontinuation Criteria

Subjects may withdraw consent at any time for any reason or be dropped from the trial at the discretion of the Investigator should any untoward effect occur. In addition, a subject may be withdrawn by the Investigator or the Sponsor if enrollment into the trial is inappropriate, the trial plan is violated, or for administrative and/or other safety reasons. Specific details regarding discontinuation or withdrawal are provided in Section 7.1.3 – Other Procedures.

A subject must be discontinued from the trial for any of the following reasons:

- AE as described above (section 5.3.2.3).
- The subject or legal representative (such as a parent or legal guardian) withdraws consent.
- Confirmed radiographic disease progression

Note: A subject may be granted an exception to continue on treatment with confirmed radiographic progression if clinically stable or clinically improved, please see Section 5.3.2.4

- Any clinical adverse event (AE), laboratory abnormality or intercurrent illness which, in the opinion of the investigator, indicates that continued participation in the study is not in the best interest of the subject
- Intercurrent illness that prevents further administration of treatment
- Investigator's decision to withdraw the subject
- The subject has a confirmed positive serum pregnancy test
- Noncompliance with trial treatment or procedure requirements
- The subject is lost to follow-up

- Administrative reasons

The End of Treatment visit procedures are listed in Section 6 (Protocol Flow Chart) and Section 7. After the end of treatment, each subject will be followed for 30 days for adverse event monitoring. Subjects who discontinue for reasons other than progressive disease will have post-treatment follow-up for disease status until disease progression, starting a non-study cancer treatment, withdrawing consent or becoming lost to follow-up. After documented disease progression, information on survival will be obtained until death, withdrawal of consent, or the end of the study, whichever occurs first.

5.6 Clinical Criteria for Early Trial Termination

Early trial termination will be the result of the criteria specified below:

1. Quality or quantity of data recording is inaccurate or incomplete
2. Poor adherence to protocol and regulatory requirements
3. Incidence or severity of adverse drug reaction in this or other studies indicates a potential health hazard to subjects
4. Plans to modify or discontinue the development of the study drug

In the event of BMS decision to no longer supply study drug, ample notification will be provided so that appropriate adjustments to subject treatment can be made.

6.0 OUTCOME MEASURES

6.1 Primary Outcome Measures

- Incidence, nature, and severity of adverse events graded according to NCI CTCAE v4.0.
- Changes in vital signs, physical findings, and clinical laboratory results

6.2 Secondary Outcome Measures

- PFS, defined as the time from inclusion to the time of radiographic progression (as assessed by RECIST) or death from any cause during the study
- Overall survival (OS), defined as the time from the date of inclusion to the date of death from any cause
- Objective tumor response rate (ORR), defined as the proportion of patients with an objective tumor response (either partial response [PR] or complete response [CR] per investigator using RECIST)
- Durable response rate (DRR), defined as the proportion of patients with an objective tumor response lasting at least 6 months
- Duration of objective response (DOR) among patients with an objective response
- PFS, ORR, DRR and DOR assessed by irRECIST v1.1

7.0 TRIAL FLOWCHART

Trial Period:	Screening Phase		Treatment phase ^a						Post-Treatment			
	Informed consent (Visit 1)	Main Study Screening (Visit 2)	C1 D1	C2 D1	C3 D1	To be repeated until total treatment time of 12 months		Treatment discontinuation	Safety Follow-up	Follow-up Year 1 after disc.	Follow-up Year 2-4 after disc.	Survival Follow-up
Scheduling Window (Days):		-14 to -1	± 3	± 3	± 3	± 3	± 3	At time of disc.	30 days post disc.	Every 3 months post disc.	Every 6 months	
Administrative Procedures												
Informed Consent ^b	x											
Inclusion/Exclusion Criteria		x										
Demographics and Medical History		x										
Prior and Concomitant Medication Review ^c		x										
Post-study anticancer therapy status										x	x	
Clinical Procedures/Assessments												
Review Adverse Events ^{d,e}		x	x	x	x	x	x	X	x	x		
Full Physical Examination		x					x		x			
Directed Physical Examination			x	x	x		x	X		x	x	
Vital Signs and Weight ^f		x	x	x	x	x	x	X	x	x	x	
ECOG Performance Status		x	x	x	x	x	x	X	x	x	x	
Electrocardiogram (ECG) ^f		x						x ^f				
Survival Follow-up												x
Laboratory Procedures/Assessments: analysis performed by local laboratory												
Pregnancy Test ^g		x						x				
PT/INR and aPTT ^h		x										
CBC with Differential ⁱ		x	x	x	x	x	x	X	x	x	x	
Comprehensive Serum Chemistry Panel ⁱ		x	x	x	x	x	x	X	x	x	x	
HIV, HBV and HCV test		x										
Urine analysis ⁱ		x					x	X	x	x ^l	x	
FT4 and TSH, anti TPO ^{ip}		x			x			X	x	x	x	
Treatment administration												
Nivolumab			x	x	x	x	x					
Radiation therapy				x	x							
Efficacy Measurements												
18F-FDG PET/CT ^j		x						x ^k	x ^m			
Tumor Biopsies/Archival Tissue Collection/Correlative Studies Blood												
Archival and Newly Obtained Tissue Collection ⁿ		x		x ^r	x ^r			x ^r				
Plasma and Serum Collection ^o		x		x	x	x	x	X		x ^l	x	

Trial Period:	Screening Phase		Treatment phase ^a						Post-Treatment			
Treatment Cycle (C)/Title: (Each cycle is 2 weeks)	Informed consent (Visit 1)	Main Study Screening (Visit 2)	C1	C2	C3	To be repeated until total treatment time of 12 months		Treatment discontinuation	Safety Follow-up	Follow-up Year 1 after disc.	Follow-up Year 2-4 after disc.	Survival Follow-up
D1			D1	D1	C4	C5	D1					
Scheduling Window (Days):		-14 to -1	± 3	± 3	± 3	± 3	± 3	At time of disc.	30 days post disc.	Every 3 months post disc.	Every 6 months	
PBMC collection ^o		x		x	x		x	X		x ¹		

- a. General, assessments/procedures are to be performed on Day 1 and prior to the first dose of treatment for each cycle unless otherwise specified. Treatment cycles are 2 weeks; however the treatment cycle interval may be increased due to toxicity according to the dose modification guidelines.
- b. Written consent must be obtained prior to performing any protocol specified procedure. Results of a test performed prior to the subject signing consent as part of routine clinical management are acceptable in lieu of a screening test if performed within the specified time frame in the protocol. Subject number will be assigned when the study informed consent is signed.
- c. Prior medications – Record all medications taken within 30 days of screening visit. Concomitant medications – Enter new medications started during the trial through the Safety Follow-up visit. Record all medications taken for AEs.
- d. AEs and laboratory safety measurements will be graded per NCI CTCAE version 4.0. All AEs, whether gradable by CTCAE or not, will also be evaluated for seriousness.
- e. After informed consent has been obtained but prior to initiation of study drug, only serious adverse events caused by a protocol-mandated intervention should be reported. After initiation of study drug, all adverse events will be reported until 90 days after the last dose of study treatment or until initiation of another anti-cancer therapy, whichever occurs first. After this period, investigators should report any serious adverse events that are believed to be related to prior treatment with study drug. For subjects included and never treated with study drug, SAEs should be collected for 30 days from the date of inclusion. All SAEs must be followed to resolution or stabilization.
- f. Vital signs to include temperature, pulse, oxygen saturation, weight and blood pressure. Height will be measured at screening only. ECG is to be performed at screening, C5 day 1 and every 8th week thereafter, until disease progression or end of treatment with nivolumab.
- g. For women of childbearing potential, a serum pregnancy test should be performed within 24 hours prior to first dose of trial treatment. Pregnancy tests (serum and/or urine tests) should be repeated every 5 cycles (10 weeks) ± 7 days.
- h. Coagulation factors (PT/INR and aPTT) should be tested as part of the screening procedures for all subjects. Any subject receiving anticoagulant therapy should have coagulation factors monitored closely throughout the trial.
- i. Unresolved abnormal lab values that are drug related AEs should be followed until resolution. Lab tests do not need to be repeated after the end of treatment if lab tests are within normal range.
- j. Tumor assessments by 18F-FDG PET/CT will be performed at screening, (Cycle 7), (Cycle 16) and at Month 12 (± 1 week). Tumor response will be evaluated using both and RECIST v1.1 (Appendix 15.3) and immune-modified RECIST criteria (Appendix 15.4). In the absence of disease progression, tumor assessments should continue regardless of whether patients discontinue study treatment, unless they withdraw consent or the study is terminated by the Sponsor, whichever occurs first.
- k. Cycle 7 and Cycle 16, Month 12 and yearly thereafter until 5 years after start of treatment
- l. For patients not progressed during treatment, urine analysis, plasma and serum, and PBMC collection to be performed at first FU visit only (12 weeks after discontinuation).
- m. In subjects who discontinue study therapy, a radiologic evaluation should be performed at the time of treatment discontinuation (i.e., date of discontinuation ± 4 weeks). If a previous scan was obtained within 4 weeks prior to the date of discontinuation, then a scan at treatment discontinuation is not mandatory.
- n. Fresh frozen and FFPE tumor biopsies before start of treatment (Cycle 1), before start of radiotherapy (Cycle 2), at Cycle 3 and at disease relapse/progression.
- o. PBMC; at screening (or day 1 Cycle 1), and at Day 1 at the following cycles; Cycle 2, Cycle 3, Cycle 5, Cycle 9, Cycle 16 and at disease progression. 100 ml ACD blood at baseline. 50 ml ACD blood at later time points. To be taken before infusion of IMP. Plasma and serum will be collected at screening (or day 1 Cycle 1), Cycle 2 (Day 1 and 8), Cycle 3 (Day 1 and 8), Cycle 4 (Day 1), Cycle 5 (Day 1), Cycle 9 (Day 1), Cycle 16 (Day 1), Month 12 and at disease progression.
- p. Thyroid function testing is to be done every 6 weeks during nivolumab treatment.
- r. The sample collection is optional

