Despite aggressive multimodal treatment with chemoradiotherapy, hypoxic-modulators and surgery to cure HNSCC patients, recurrent and second primary tumors in previous irradiated area (>46 Gy) are a common clinical challenge. Re-irradiation to doses of 60 Gy or more is a possible treatment option, offering long-term survival for selected patients. However, the re-irradiation is complicated with serious acute and late toxicity. Recurrent disease is also associated with a high risk of developing systemic disease. There is a need for new treatment approaches and combinations to improve tumor control and reduce toxicity.

Radiotherapy is a powerful inducer of inflammation, and the expression of PD1-L1 is known to be enhanced by inflammatory cytokines, including IFN γ . Experimental evidence from mice

models have shown that radiotherapy induces increased PD-L1 expression in tumor tissue. Moreover, there is evidence suggesting that HNSCC with T-cell infiltration is more sensitive to radiotherapy. There is thus a strong rationale for combining PD-1 inhibitors with radiotherapy. However, this potential remains largely unexplored in humans. We consider that head-and-neck cancer is a particularly attractive entity for investigating this therapeutic combination, because of i) the high radiosensitivity of this cancer form ii) the clinical efficacy of PD-1 inhibitors as monotherapy in early clinical trials iii) the availability of tumor biopsies for translational/biomarker research.

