4.0 OBJECTIVES & HYPOTHESES

4.1 Objectives

Primary objectives:

- 1) To determine the safety and tolerability of nivolumab when administered concomitant with high dose (60 Gy) re-irradiation in patients with locally advanced recurrent or second primary HNSCC
- 2) To determine a safe dose of nivolumab when administered concomitant with high dose (60 Gy) re-irradiation in patients with locally advanced recurrent or second primary HNSCC

Secondary objectives:

- 1) To evaluate progression-free survival after 12 months
- 2) To evaluate objective response rate (ORR) and duration of response (DOR), by RECIST v1.1 as primary method and immune-related RECIST (irRECIST) as secondary method
- 3) To evaluate overall survival

Exploratory objectives:

- 4) To investigate the immunological response, tumor evolution and dynamics in the tumor microenvironment induced by the study therapy
- 5) To investigate biomarkers for development of clinical response, toxicity and immune response

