5.2 Study treatment

The study will include 20 patients. The following treatment will be used:

- Radiotherapy (RT) to a total dose of 60 Gy, given as 1.5 Gy fractions twice daily for a total period of 4 weeks, will be delivered to the target volumes determined by PET-CT scan. Definition of target volumes and organs at risk will follow the Dahanca guidelines 2013 (published on www.dahanca.dk). The dose delivered to organs at risk, determined by PET-CT scan, will also be calculated.
- Nivolumab administered intravenous every two weeks, starting two weeks (Cycle 1, Day 1) before start of radiotherapy. Nivolumab will be given for a maximum of 12 months or until disease progression.
- Nivolumab will be administered according to a dose escalation schedule (1.0 and 3.0 mg/kg), as shown in Figure 1. Three patients will be included at each dose level. During the dose escalation part the subsequent patient will start therapy with nivolumab 6 weeks after the previous to allow time to observe the possibility for acute toxicity. If no dose limiting toxicity (DLT) is observed at the first dose level, additional three patients will be included at the next dose level. If DLT is experienced see section 8.8 for details. The remaining patients will be treated at the maximum tolerated dose.
- The nivolumab dose will be adjusted to 3.0 mg/kg (standard dose used in NCT02105636) for all patients from Cycle 5, Day 1 (2 weeks after end of radiotherapy), irrespective of starting dose.

The study treatment is outlined in Table 1. Trial treatment should begin within 28 days of first interventional screening assessments. Details on preparation and administration of nivolumab are provided in the IB.

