5.2.1 Study drug

The product storage manager at the local pharmacy should ensure that the study drug is stored in accordance with the environmental conditions (temperature, light, and humidity) as determined by BMS. If concerns regarding the quality or appearance of the study drug arise, the study drug should not be dispensed and contact BMS immediately.

Investigational product documentation must be maintained. That includes all processes required to ensure drug is accurately administered. This includes documentation of drug storage,

administration and, as applicable, storage temperatures, reconstitution, and use of required processes (eg, required diluents, administration sets).

Infusion-related supplies (eg, IV bags, in-line filters, 0.9% sodium chloride injection, 5% dextrose injection) will not be supplied by the sponsor and should be purchased locally if permitted by local regulations.

The investigational product should be stored in a secure area according to local regulations. It is the responsibility of the investigator to ensure that investigational product is only dispensed to study subjects. The investigational product must be dispensed only from official study sites by authorized personnel according to local regulations.

[figure not shown]
Please refer to the current version of the Investigator Brochure (IB) and/or pharmacy reference sheets for complete storage, handling, dispensing, and infusion information for nivolumab.

The infusion will be administered by nurses with experience in treatment with immunotherapy.

Table 1 Study Treatment

Drug	Dose/Potency	Dose Frequency	Route of Administration	Regimen/Treatment Period	Use
Nivolumab	1,0 mg/kg	Q2W	IV infusion	Day 1 of each 2 week cycle	Experimental, Dose level 1
Nivolumab	3,0 mg/kg	Q2W	IV infusion	Day 1 of each 2 week cycle	Experimental, Dose level 2
Radiotherapy	1,5 Gy	BID		5 days a week, 4 weeks (Cycle 2 and 3)	Standard

Figure 1

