8.1.3.4.2 Follow-up Visits

Subjects who discontinue trial treatment for a reason other than disease progression will move into the Follow-Up Phase. The remaining patients will move into the FollowUp Phase after end of nivolumab treatment. The patients should be assessed every 3 months the first year after discontinuation (± 7 days), the following three years (year 2-4 after discontinuation of study treatment) every six month, to monitor disease status. Every effort should be made to collect information regarding disease status until the start of new anti-neoplastic therapy, disease progression, death and end of the study. Information regarding post-study anti-neoplastic treatment will be collected if new treatment is initiated.

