9.3 Nonserious Adverse Events

9.3.1 Nonserious Adverse Event Collection and Reporting

The collection of nonserious AE information should begin at initiation of study drug until 90 days from the last dose of study drug.

Nonserious AEs should be followed to resolution or stabilization, or reported as SAEs if they become serious. Follow-up is also required for nonserious AEs that cause interruption or discontinuation of study drug and for those present at the end of study treatment as appropriate. All identified nonserious AEs must be recorded and described on the nonserious AE page of the CRF.

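### No adverse-event collection window is anchored to radiotherapy, the 30-day, 90-day and Follow-up Year 1 rules conflict, and the Year 2-4 visits carry no adverse-event review, although late re-irradiation toxicity is a named risk

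*Combined protocol and SAP*

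**What the plan says.** Section 4.1 gives the first primary objective as "To determine the safety and tolerability of nivolumab when administered concomitant with high dose (60 Gy) re-irradiation". Section 2.1 states that "the re-irradiation is complicated with serious acute and late toxicity". The rules on how long AEs are collected are spread over several places:

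- **Section 7.0, footnote e** (attached to the AE review row): "After initiation of study drug, all adverse events will be reported until 90 days after the last dose of study treatment", or until another anti-cancer therapy starts, if sooner. After that, "investigators should report any serious adverse events that are believed to be related to prior treatment with study drug".
- **Section 9.3.1:** "The collection of nonserious AE information should begin at initiation of study drug until 90 days from the last dose of study drug".
- **Section 9.2.1:** SAEs are collected to 90 days after the last nivolumab dose. Later SAEs are reported if thought related to study drug or to a protocol-specified procedure.
- **Sections 1.0, 5.5 and 8.1.3.4.1:** AE monitoring to 30 days after treatment. Sections 1.0 and 8.1.3.4.1 keep 90 days for SAEs.
- **Section 7.0, flowchart row for AE review:** marked through Follow-up Year 1, blank for Years 2-4 and for survival follow-up. Directed physical examination, vital signs, ECOG status and laboratory tests are marked in Years 2-4.
- **Section 8.1.3.4.2:** the later visits take place "the following three years (year 2-4 after discontinuation of study treatment) every six month, to monitor disease status".
- **Section 9.0:** the causal relationship is assessed against study drug, with no category for radiotherapy.
- **Section 9.9:** significant worsening noted at physical examinations or other safety assessments is to be recorded as an AE. No time limit is given.

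**The concern.** The hazard that the protocol names belongs to the radiotherapy, but the AE clock is set by the drug. How long a patient is watched after re-irradiation therefore depends on how long nivolumab continued. It is shortest in those who stopped early, including those who stopped for toxicity.

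Section 11.1 summarises the primary outcome as plain proportions, without reference to observation time. Unequal observation would pass directly into the reported AE incidence, and late events would tend to be under-counted. Because the sections also disagree on when collection stops, two investigators could follow the protocol in good faith and record different things at the same visit.

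**Working it through.** **Inputs.** Take the first nivolumab dose as day 0. Nivolumab is given every 2 weeks, "starting two weeks (Cycle 1, Day 1) before start of radiotherapy" (section 5.2), so radiotherapy starts on day 14. It lasts 4 weeks, in Cycles 2 and 3 (Table 1), so it ends at about day 42. Nivolumab lasts at most 12 months, so the last dose falls on about day 350 (Cycle 26) to day 365. One month is 30.44 days.

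**The plan's own figures.** 60 Gy / 1.5 Gy = 40 fractions; 40 / 2 per day = 20 treatment days; 20 / 5 per week = 4 weeks. Cycle 5 Day 1 is day 4 × 14 = 56, and 56 − 42 = 14 days. This agrees with section 5.2, which puts Cycle 5 Day 1 two weeks after the end of radiotherapy.

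**Observation after radiotherapy** = day of last nivolumab dose + length of window − 42. For Follow-up Year 1 the length is 365 days.

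| Last nivolumab dose | 90-day rule, days (months) | 30-day wording, days (months) | AE review to end of Follow-up Year 1, days (months) |
|---|---|---|---|
| Cycle 1, day 0 | 48 (1.6) | −12 (−0.4) | 323 (10.6) |
| Cycle 4, day 42 | 90 (3.0) | 30 (1.0) | 365 (12.0) |
| Cycle 16, day 210 | 258 (8.5) | 198 (6.5) | 533 (17.5) |
| Cycle 26, day 350 | 398 (13.1) | 338 (11.1) | 673 (22.1) |
| Month 12, day 365 | 413 (13.6) | 353 (11.6) | 688 (22.6) |

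The negative entry means that, read literally, collection would stop 12 days before radiotherapy ended. Counting radiotherapy as ending on its 20th weekday (day 39) adds 3 days to every entry.

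**Reading of study treatment.** Section 5.2 and Table 1, both headed study treatment, list radiotherapy. If footnote e uses the term in that sense, its 90 days cannot end before 90 / 30.44 = 3.0 months after completed radiotherapy, unless new anti-cancer therapy starts. Sections 9.2.1 and 9.3.1 do not allow this reading, because they name nivolumab and study drug.

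**Spread.** Leaving out the Cycle 1 extreme and comparing a last dose at Cycle 4 with one at Cycle 26, 398 / 90 = 4.4-fold under the 90-day rule.

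**What Years 2-4 would add.** Six-monthly visits over three years make 3 × 2 = 6 visits. The Year 4 visit falls at last dose + 4 × 365.25 − 42 days: 1419 days (46.6 months) after radiotherapy for a last dose on day 0, and 1784 days (58.6 months) for one on day 365.

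**The case against.** The other side has five fair arguments.

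1. **Follow-up Year 1.** A reader might infer that late toxicity is observed for only 1.6 to 13 months. The flowchart does not support that. AE review is marked at the 3-monthly Year 1 visits, and section 8.1.3.4.2 sends patients who stop without progression into that phase, including those who stop for toxicity. Review then reaches about 10.6 to 22.6 months after radiotherapy, without progression or new therapy. This stands. But footnote e, on the same row, ends routine reporting at 90 days, so what must be recorded at those visits is unclear.

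2. **Late SAEs.** It is tempting to say that late SAEs are tied to the drug alone. That is true of footnote e only. Section 9.2.1 adds protocol-specified procedures, and radiotherapy may count as one. The text does not say so, its one example of a later procedure is a follow-up biopsy, and non-serious events are not reached.

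3. **Events found at examination.** A reader might conclude that a non-serious late effect would never be recorded. Section 9.9 may capture worsening seen at an examination, and sections 8.1.3.4.1 and 9.3.1 keep AEs that are already open under follow-up. This stands too, but none of it sets up a systematic review for new late toxicity.

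4. **Purpose of the trial.** Section 2.3 expects any added toxicity within 2 weeks after radiotherapy, Table 1 labels radiotherapy standard, and 20 uncontrolled patients cannot separate nivolumab-enhanced late effects from those of re-irradiation alone. The last point limits interpretation. The expectation itself can be checked only by looking later.

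5. **Reach of the remedy.** Patients with confirmed progression or new therapy move to survival follow-up by telephone or through their doctor or local hospital (section 8.1.3.4.3), so no change at the follow-up visits gives equal observation. This stands.

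**Conclusion.** The point holds as a gap in collection and a conflict between sections, and it should be corrected because it bears on the primary outcome. No AE window is anchored to radiotherapy. Under sections 9.2.1 and 9.3.1, routine collection ends about 1.6 to 13 months after radiotherapy. The 1.6 months assumes a single nivolumab dose with radiotherapy still completed, on the nominal schedule without delays. It is not a firm floor, because under footnote e a new anti-cancer therapy ends collection earlier. If footnote e covers radiotherapy, its minimum is about 3.0 months, with that same exception.

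The 30-day, 90-day and Follow-up Year 1 statements cannot all be followed. AE review is absent from the six Year 2-4 visits, and radiotherapy is missing from the causality assessment. The documents do not show that late events would go wholly unrecorded, nor that the trial would reach a wrong conclusion on tolerability, since the analysis is descriptive.

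**What to change.** - Mark AE review at the existing Year 2-4 visits in the flowchart.
- At every scheduled follow-up visit, record Grade 3 or higher AEs and all SAEs judged related to study radiotherapy or to the combination.
- Name study radiotherapy in the late-SAE rule of footnote e and section 9.2.1, and in the causality assessment of section 9.0.
- Reconcile the 30-day statements (sections 1.0, 5.5, 8.1.3.4.1), the 90-day statements (footnote e, sections 9.2.1, 9.3.1) and the Year 1 mark. State whether study treatment in footnote e includes radiotherapy.
- In section 11.1, report late events by time from the end of radiotherapy, together with each patient's observation time.
- State that patients in survival follow-up are not covered by these visits, so observation will still differ between patients.

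The cost is protocol wording, a case report form entry at visits that already include a physical examination, and some extra AE entry for at most 20 patients. No new visit or procedure is needed.
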